The study will test 3 fazirsiran dose levels compared to placebo. Patients who have signed an Institutional Review Board (IRB)/Ethics Committee (EC)-approved informed consent and have met all the protocol eligibility criteria during Screening will be assigned to one of 3 cohorts and randomized 2:1 (active: placebo) within each cohort. The 3 cohorts of the study are as follows:

- Cohort 1: 25 mg dose of fazirsiran or placebo
- Cohort 2: 100 mg dose of fazirsiran or placebo
- Cohort 3: 200 mg dose of fazirsiran or placebo

Within each cohort, requirements for biopsies, dosing schedules, and SOA will be determined based on the patient's fibrosis score during Screening.

Patients with no evidence of fibrosis

Patients who have a documented biopsy showing no evidence of fibrosis within 1 year of the Screening visit will not require liver biopsy at any point during the study.

Patients without fibrosis at Screening will receive 2 doses of fazirsiran or placebo on Day 1 and Week 4, as per the SOA. Following their Week 4 dose, these patients remain in the study with regular visits per the SOA until Week 64.

Patients with evidence of fibrosis

[figure not shown]
Patients who have a pre-dose biopsy showing evidence of fibrosis (without definitive cirrhosis) during Screening will have a post-dose biopsy performed at Week 48. If a patient is beyond Week 48 at the time of IRB/EC approval of Protocol v4.0, then the post-dose biopsy will occur at Week 72 or 96. The study will end after the last patient with fibrosis receives their 10th dose (Week 100 visit) or until a long-term extension study is available at the subject's study site, whichever comes first.

Patients with evidence of fibrosis at Screening will receive a dose on Day 1, Week 4, and Week 16, then every 12 weeks for up to 18 doses total.

Dose Evaluation and Selection

After all enrolled patients completed the Week 16 visit, an Interim Analysis was performed to select a single dose level (25, 100, or 200 mg) for the open-label phase of the study. Based on cumulative safety, efficacy, and pharmacodynamic (PD) data from the fazirsiran clinical program (clinical studies AROAAT1001, AROAAT2001, and AROAAT2002), a fazirsiran dose (200 mg) was selected by the Sponsor. All patients with fibrosis at Screening who completed the post-dose biopsy visit will receive fazirsiran at the selected dose for the duration of the study (open-label phase) but will remain blinded to the randomized treatment assignment.

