- Percent change in expression of liver fibrosis associated genes
- Percent change in *SERPINA1* messenger RNA (mRNA) levels
- Change in measures of fibrosis (Metavir fibrosis stage)
- Change in liver histology (e.g., globules, inflammation, steatosis)
- Measures of hepatic injury including ALT, GGT, and AST
- Change in MRI (where available and if feasible)
- Change in FibroScan® (where available)
- Serum fibrosis biomarkers (PRO-C3/PRO-C6), FIB-4, APRI

Pharmacokinetic Assessments:

Blood samples will be collected from all enrolled patients for sparse sampling plasma pharmacokinetic (PK) analysis after dose 1 (all patients) and 3 (fibrosis subset) per the SOA.

Immunogenicity Assessments:

Emergence of ADAs will be evaluated with samples drawn per the SOA.

Statistical Considerations: The objective of this Phase 2 study is to evaluate 3 dose levels relative to placebo and select a dose level to be used in the open-label phase of this study and in later stages of development based on the evaluation of safety, as well as percent change from baseline in serum Z-AAT levels. The primary efficacy analysis, executed after the last patient completes Week 16 visit, will evaluate the difference in mean percent change from baseline at Week 16 between each active dose group and the pooled placebo groups. The primary efficacy analysis, performed using the mixed model repeated measures (MMRM) approach, will be

executed in all randomized patients who receive at least one dose of study treatment (Full Analysis Set), regardless of the total number of received doses. With a total sample size of approximately 36, the study has 99% global power to declare at least one treatment dose group as different from placebo, assuming the treatment difference from placebo of at least 70 percent points (SD=35) and using a one-sided 2.5% level of significance with Hochberg's adjustment for multiplicity of testing. Details of planned statistical analysis will be provided in the statistical analysis plan (SAP).

Extended Efficacy Analysis will be performed after the last patient with fibrosis reaches the post-baseline biopsy visit. Patients will receive the treatment dose selected following the Week 16 Interim Analysis, only after the patient has completed the post-baseline biopsy visit (Week 48, 72, or 96). Final Analysis will be performed after all patients complete either an Early Termination or Study Completion visit and database lock.

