The AROAAT2001 design and conduct is supported by existing nonclinical pharmacology and toxicology data as well as data from a Phase 1 clinical study AROAAT1001 in healthy volunteers which evaluated safety, PK, and PD effect of single and multiple escalating doses of fazirsiran. AATD patients with AATD associated liver disease will require multiple doses of fazirsiran to sustain hepatic silencing of AAT production. Accordingly, this study uses multiple doses of fazirsiran with each dose after the second dose administered approximately every 3 months.

Three different dose levels are being tested. The dosing regimen utilized in this study is supported by the PD effect and safety profile of three once every 28 days (Q28) doses of fazirsiran, which was evaluated in the AROAAT1001 study. Single dose PD effect from the AROAAT1001 study indicates that AAT serum protein levels generally reach nadir, but not always full suppression to below lower limit of quantitation around Week 6 to 8 and start to rebound by approximately Week 12 after a single dose. This observed time until rebound supports quarterly dosing. This study also demonstrated that a second dose at Day 29 (4 weeks after initial dose) resulted in complete suppression of circulating AAT levels that was sustained. (See Investigator's Brochure for details.) Based on these results, it was determined that 2 doses administered 28 days apart would quickly lead to maximal and sustained reduction in hepatic AAT production but thereafter dosing could be quarterly. Hence, this was viewed as the best approach to achieve the fullest level of hepatic reduction of the insulting agent while minimizing overall patient exposure by moving to quarterly dosing.

Based on non-clinical studies in the PiZ mouse model and experience with liver recovery from other necro-inflammatory diseases such as viral hepatitis, it is highly likely that dose administration beyond 3 doses will be required to reduce insoluble aggregated liver Z-AAT sufficiently to reduce globule inflammation and hopefully allow repair of hepatic architecture. Based on other precedents as discussed above, improvement of fibrosis or other adverse liver histologic findings due to AATD liver disease may require long-term therapy to show improvement.

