After all enrolled patients completed the Week 16 visit, an Interim Analysis was performed to select a single dose level (25, 100, or 200 mg) for the open-label phase of the study. Based on cumulative safety, efficacy, and PD data from the fazirsiran clinical program (clinical studies AROAAT1001, AROAAT2001, and AROAAT2002), a fazirsiran dose (200 mg) was selected

by the Sponsor. All patients with fibrosis at Screening who completed the post-dose biopsy visit at Week 48 (or Week 72 or 96) will receive fazirsiran at the selected dose for the duration of the study (open-label phase) but will remain blinded to their randomized treatment assignment.

Figure 1: Study Schema

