6.2. Rationale for Study Design

The study is intended select a dose to be used in later stage development clinical studies and to collect noninvasive markers of liver disease alongside liver biopsy data to demonstrate the relationship of reduction of intrahepatic Z-AAT protein levels to improvement in biomarkers of liver disease. Tissue samples from percutaneous liver biopsy will be required. Other markers of liver injury such as fibrosis score will also be measured on biopsy. Biopsy will be conducted predose and post-dose for patients with evidence of fibrosis at Screening. The study will enroll PiZZ patients without definitive cirrhosis. Patients without evidence of fibrosis will be able to participate in a limited portion of the study. The study uses a placebo arm to help evaluate the safety of fazirsiran in an AATD patient population. The study is double-blind to limit the occurrence of conscious and unconscious bias in trial conduct and interpretation. Blinding will be achieved using a placebo (PBO) (0.9% normal saline) volume matched injection. Inclusion of patients receiving PBO will reduce bias in the assessment of drug safety and tolerability.

In the study, 3 separate dose levels are used to test if there is a dose-response in safety and PD assessments. After all enrolled patients completed the Week 16 visit, an Interim Analysis was performed to facilitate the dose selection. As changes in serum Z-AAT levels in response to fazirsiran is the primary objective of the study, any patient who does not have cirrhosis is eligible to participate. Dose and PD response in patients with cirrhosis will be studied in a separate trial designed for a hepatic impairment population.

Non-cirrhotic PiZZ AATD patients are an appropriate population to conduct dose-finding as serum Z-AAT is readily measured and levels are uninfluenced by fibrosis stage. Thus, all PiZZ patients (without definitive cirrhosis) can participate. Patients without evidence of fibrosis will only receive 2 doses and will not have a post-dose biopsy or continue into the open-label phase as they have no evidence of fibrosis and would be likely to have minimal to no histological

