11. DATA ANALYSIS AND STATISTICAL CONSIDERATIONS

Statistical analyses and descriptive summaries will be presented for primary, secondary, and exploratory endpoints using appropriate methods. A detailed statistical analysis plan (SAP) will be provided. Descriptive statistics will be presented for all analyses unless otherwise specified. For continuous variables, data will be presented as number (n), mean, median, standard deviation, minimum, and maximum. Discrete variables will be presented as frequencies and proportions or percent. Data will be analyzed by cohort and treatment groups of fazirsiran 25, 100, and 200 mg versus pooled placebo. Data summarized in tables and figures will also be presented in patient listings.

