11.10. Analysis Methods

The primary objective of the study is to evaluate the 3 doses of fazirsiran versus placebo and select a single active dose to be evaluated further in later stage studies and used in the open-label phase of this study. In addition to examination of safety, dose selection will be based on the evaluation of the mean percent change from baseline (Day 1, pre-dose) in serum Z-AAT levels through Week 16. The primary efficacy analysis, executed after all enrolled patients reach the Week 16 evaluation, will be performed using a MMRM approach. The repeated measures of the response are the values obtained at the scheduled study Weeks 2, 4, 6, and 16. The model will include fixed categorical effects for treatment, time, week, treatment by week interaction, and a baseline value of serum Z-AAT as a continuous covariate. Restricted maximum likelihood estimation (REML) with an unstructured within-patient covariance structure will be used. If the model fails to converge, alternative covariance structures will be considered.

Based on the stated model, least squares (LS) estimates of the mean percent change from baseline for each treatment group, of the difference for each fazirsiran dose group and pooled placebo, and the corresponding 95% CIs will be reported for each timepoint. P-values from the Week 16 2-sided t-tests of each for each of the 3 dose groups vs placebo group will be evaluated for significance using Hochberg's step-up procedure to adjust for multiplicity of testing. Placebo group will be pooled from placebo patients in 3 dose cohorts. The primary evaluation of interest is at Week 16 timepoint, to be completed in all randomized patients who receive at least one dose

of study treatment (FAS), regardless of the total number of received doses or any intercurrent events (hypothetical estimand).

Secondary endpoints include:

- Subject incidence of treatment-emergent AEs
- Absolute and percent change from baseline in total liver Z-AAT (insoluble + soluble) protein at post-dose biopsy
- Absolute and percent change from baseline in liver Z-AAT soluble protein at postdose biopsy
- Absolute and percent change from baseline in liver Z-AAT insoluble protein at post-dose biopsy
- Absolute and percent change from baseline in liver function tests, including ALT, AST, ALP, GGT, total bilirubin, direct bilirubin and INR at Week 16 and over time through EOS
- Absolute and percent change in serum Z-AAT overtime through EOS

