- Change over time in PK measurements of fazirsiran at timepoints specified in the SOA
- Incidence of ADAs
- Change from baseline in Metavir fibrosis stage at post-dose biopsy

If the post-dose liver biopsy is not available, the biopsy completed at Early Termination may be used.

For continuous secondary endpoints, analyses similar to the primary endpoint analysis will be performed. For all continuous longitudinal measures where data is collected at baseline and at more than one pre-scheduled post-baseline visits, a mixed-effects model repeated measures (MMRM) will be applied to evaluate the change from baseline at scheduled visits.

Prior to each analysis of continuous endpoints, the endpoint variable will be evaluated for normality, and as a result, the original data may be transformed to achieve approximate normality. Results of analysis model from transformed data will be appropriately back-transformed to original scale for reporting purpose.

Demographic, PK, PD and safety parameters will be summarized using descriptive statistics (n, mean, SD, % coefficient of variation (CV), geometric mean, geometric %CV, minimum, median, and maximum for continuous parameters; frequency and percentage for categorical parameters).

Sensitivity Analyses of Primary Efficacy Objective

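### In the Protocol and SAP addendum, by-arm serum Z-AAT and liver-test estimates after Week 16 pool two dosing schedules, and the augmentation comparison has no stated cut at first open-label dose

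*Protocol*

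**What the plan says.** **Schedules.** The Protocol Synopsis states: "Patients with evidence of fibrosis at Screening will receive a dose on Day 1, Week 4, and Week 16, then every 12 weeks". Protocol 6.2 states: "Patients without evidence of fibrosis will only receive 2 doses and will not have a post-dose biopsy or continue into the open-label phase". Both schedules of assessments (Tables 1 and 2) collect Z-AAT and clinical laboratory samples at Weeks 28, 40, 52 and 64. Protocol 7.1 requires at least 24 of about 36 patients to have fibrosis, so at most 12 follow the two-dose schedule.

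**Analysis.** Protocol 11 sets the groups: "Data will be analyzed by cohort and treatment groups of fazirsiran 25, 100, and 200 mg versus pooled placebo". Protocol 11.10 gives the primary repeated-measures model terms for treatment, time, week, treatment by week and baseline Z-AAT. It then extends the approach: "For continuous secondary endpoints, analyses similar to the primary endpoint analysis will be performed". The secondary list includes "Absolute and percent change in serum Z-AAT overtime through EOS", and liver tests over the same span. Fibrosis status is not a stratification factor (11.3). The nearest subgroup is Metavir 0–1 against 2–3 (11.9).

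**Open-label switch.** Under Protocol 6.1, fibrosis patients who complete the post-dose biopsy visit move to the selected dose, 200 mg, whatever their randomised arm. The Synopsis times this: "only after the patient has completed the post-baseline biopsy visit (Week 48, 72, or 96").

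**Augmentation.** Protocol 9.7 counts patients on fazirsiran and on placebo who need augmentation over the whole study, and plans a Kaplan-Meier comparison of time to augmentation. Protocol 11.5 words both in terms of new initiation.

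**SAP addendum.** Section 6.1 generally puts open-label data in separate descriptive summaries, and Section 4 resets baseline at the first open-label dose. Much else is referred to SAPv3.0, which was not supplied.

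**The concern.** Taken as written, a late by-arm estimate describes neither sustained dosing nor recovery after two doses. It averages the two, with weights set by how many patients without fibrosis fell in each arm. Readers will use these curves to judge durability and compare doses over time, so the mixture matters most at the latest double-blind visits. Liver tests share the problem.

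For augmentation, a placebo patient with fibrosis may start it while receiving 200 mg. If fazirsiran raises augmentation use and such starts are counted under original arm, the whole-study count and the late part of the Kaplan-Meier comparison move toward no difference. Lung effects of lowering AAT are a named potential risk in Protocol 4.8, so this would blunt one of the readouts meant to detect them.

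**Working it through.** **1. The plan's own figure.** Protocol 11.2 uses 8 patients per active arm, 12 on placebo, a 70-point difference, SD 35 and one-sided 2.5% with Hochberg. It states 99% power for at least one dose and 97% for all doses. Simulation with a pooled-variance t-test (32 df) gives 99.8% and 97.0%, so the figures reproduce. They concern Week 16 only. The 70 points serve below as a scale.

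**2. When the schedules part.** Weeks since last dose at each pre-dose sample:

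| Visit | No fibrosis (last dose Week 4) | Fibrosis |
|---|---|---|
| Week 16 | 12 | 12 |
| Week 28 | 24 | 12 |
| Week 40 | 36 | 12 |
| Week 52 | 48 | 12 |

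The schedules agree at Week 16 and separate afterwards. Protocol 4.7 says healthy-volunteer AAT levels "start to rebound by approximately Week 12 after a single dose", so divergence is expected, but the documents do not say how fast it proceeds.

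**3. Dilution.** Let s be the two-dose share of an active arm (set at the overall share) and r the fraction of effect kept by two-dose patients (assumed).

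Observed difference = 70 × [(1 − s) + s × r]

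| No-fibrosis patients | s | Week 28, r = 0.78 | Week 52, r = 0 | Week 52, r = 0.5 |
|---|---|---|---|---|
| 12 of 36 | 0.333 | 64.9 | 46.7 | 58.3 |
| 6 of 36 | 0.167 | 67.4 | 58.3 | 64.2 |
| 4 of 36 | 0.111 | 68.3 | 62.2 | 66.1 |

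These are raw means; model-based means may differ. The documents give no input for a similar calculation on liver tests.

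**4. Chance imbalance between doses.** Under a simple random split into 8, 8, 8 and 12 (exact hypergeometric), the probability that two dose groups differ by 3 or more no-fibrosis patients is 39%, 22% or 8% with 12, 6 or 4 such patients in all. A 3-of-8 gap between equally effective doses creates an apparent difference of 70 × 3/8 × (1 − r): 5.8 points at r = 0.78, 13.1 at 0.5 and 26.2 at 0.

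**5. Does anything supplied separate the schedules?** Metavir 0–1 against 2–3 does not: stage 0 (two doses) sits with stage 1 (continued dosing). The addendum's split by Screening fibrosis status (6.3, 6.4.1) does not either. It applies to open-label data, the Open-label Phase Set requires an open-label dose (3.1), and only fibrosis patients enter that phase. The split therefore has one level there.

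**6. Augmentation.** A Week 48 biopsy makes Week 52 the first open-label dosing visit; before it, no placebo patient is on 200 mg. Assume 8 of 12 placebo patients have fibrosis, all were biopsied at Week 48, and there are no dropouts or earlier events. Share of the placebo at-risk set on 200 mg in Weeks 52–64:

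- nobody on augmentation at baseline: 8/12 = 67%
- 4 of the 8 already on it: 4/(4 + 4) = 50%
- 6 of the 8 already on it: 2/(2 + 4) = 33%

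The last two lines also assume that none of the 4 no-fibrosis patients is on it. If only half of the 8 were biopsied at Week 48, the first line becomes 4/12 = 33%.

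**The case against.** The strongest reply is that the main plan is unseen. The addendum says analyses in SAPv3.0 are not repeated, and its one-level fibrosis split may be wording carried over from a split already there. That is possible but not shown, and it would not by itself establish a split for Z-AAT. It limits the point to the supplied text.

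Second, schedule follows a baseline characteristic, so by-arm means compare assigned strategies fairly in expectation, and an analysis similar to the primary one does not forbid a fibrosis term. This stands as far as it goes. It does not make the late mean interpretable as either regimen, and with 8 per arm and no stratification by fibrosis, balance cannot be relied on.

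Third, a reader might infer that open-label data are mixed into the by-arm Z-AAT and laboratory analyses. The documents do not support that as the natural reading: addendum 6.1, 6.3 and 6.4.2 provide separate open-label summaries. What remains is schedule mixing within the double-blind data.

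Fourth, Protocol 11.1 groups the Safety Population by treatment actually received, so attributing later starts to original placebo is an interpretation. That is fair, but the section gives no rule for a patient who received both treatments. Addendum 6.4.3, which declines separate medication summaries, concerns general medication tables and does not settle the matter.

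Fifth, a reader might take augmentation as the sole comparative lung-safety readout. It is not: Protocol 9.7 also compares spirometry and DLCO and evaluates COPD exacerbations, and under Appendix 3 the DSMB reviews each patient newly started on augmentation because of lung-function decline.

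**Conclusion.** The point holds for the Protocol and SAP addendum, with moderate confidence because SAPv3.0 is unseen. The pooling is read from the analysis groups and model terms; no sentence states it outright.

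- **Z-AAT and liver tests:** dilution is slight at Week 28 (65–68 against 70) and potentially material by Week 52 (47–58 with the maximum 12 no-fibrosis patients, 62–66 with 4). The retained-effect values are assumptions; the documents say only when rebound begins. The largest false dose gap, 26 points, needs complete loss of effect as well as a 3-of-8 imbalance.
- **Augmentation:** up to 67% of the placebo at-risk set could be on 200 mg in Weeks 52–64 under the stated assumptions, and 50% or 33% with prior augmentation use, which Protocol 4.8 describes as common. The direction of bias depends on fazirsiran raising augmentation use and on counting by original arm.

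It would be wrong to infer that the primary result or the dose choice is compromised. Both schedules have had the same two doses when the Week 16 sample is taken, and scheduled post-dose biopsies are confined to fibrosis patients.

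**What to change.** For visits after Week 16, report double-blind serum Z-AAT and liver tests by the Screening fibrosis status that set the schedule: fibrosis patients by arm up to the last visit before first open-label dose, and no-fibrosis patients separately to Week 64. Leave the pre-specified Metavir subgroup as it is.

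Limit the augmentation count and Kaplan-Meier comparison to patients not on augmentation at baseline, in line with the new-initiation wording of Protocol 11.5. Censor both at first open-label dose and report later starts separately by original arm.

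Label the added tables descriptive. If SAPv3.0 already does this, citing the section is enough.

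The cost is some SAP text and a few tables. The downsides are smaller groups at late visits, shorter comparative follow-up for augmentation, and tables that are supportive only because they are added after the unblinded Week 16 analysis. No treatment rule changes.

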11.2. Sample Size Considerations

Approximately 36 patients will be enrolled and randomized in the study. The primary efficacy analysis based on serum AAT levels, will be executed after all enrolled patients complete Week 16 visit and will evaluate the difference in mean percent change from baseline at Week 16 between each active dose group and the pooled placebo groups. Patients will be randomized in a 2:1 (active:placebo) ratio within each of the 3 dose cohorts. With 8 patients in each of the 3 active treatment dose groups and 12 patients in the pooled placebo group, the study has 99% global power to declare at least one treatment dose group as different from placebo, assuming the treatment difference from placebo of at least 70 percent points and using a one-sided 2.5% level of significance with Hochberg's step-up adjustment for multiplicity of testing. Furthermore, the study has 97% conjunctive power to detect all dose groups that are truly different from placebo and 99% disjunctive power to detect at least one dose group that is truly different from placebo. The estimate of variability of the primary endpoint is calculated from prior studies to be 35%.

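### Protocol section 11.10 checks normality on the endpoint rather than on model residuals, so the drug effect can feed into the choice of analysis scale; the excess is small at the planning values

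*Protocol*

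**What the plan says.** Protocol section 11.10 (Analysis Methods) sets the timing and scope of the check, "Prior to each analysis of continuous endpoints", and then its object and consequence: "the endpoint variable will be evaluated for normality, and as a result, the original data may be transformed to achieve approximate normality". It adds: "Results of analysis model from transformed data will be appropriately back-transformed to original scale for reporting purpose". It names no test, threshold or transformation. It mentions neither residuals nor a check within each arm.

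The same section defines the primary analysis as an MMRM on percent change in serum Z-AAT, using four post-baseline visits up to Week 16, with these terms: "The model will include fixed categorical effects for treatment, time, week, treatment by week interaction, and a baseline value of serum Z-AAT". Dose selection is to rest, besides safety, on the mean percent change.

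Section 11.2 (Sample Size Considerations) supplies the planning values: "With 8 patients in each of the 3 active treatment dose groups and 12 patients in the pooled placebo group", "assuming the treatment difference from placebo of at least 70 percent points", and "The estimate of variability of the primary endpoint is calculated from prior studies to be 35" per cent.

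The supplied SAP is an addendum on descriptive summaries for the open-label phase. It refers to SAPv3.0 for everything else and says nothing on normality checks.

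**The concern.** The MMRM does not need a normal endpoint over all patients. It needs approximately normal residuals once treatment, week, their interaction and baseline are accounted for. Before the model is fitted, the endpoint still contains the treatment effect. Twenty-four of 36 patients are expected to sit 70 or more points below the other 12, so the pooled values form a mixture even when every error is normal.

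Two things follow. The check looks at the wrong quantity, and its result depends partly on how well the drug works. And because the transformation is left open, the scale of the primary analysis may be settled only after the data are seen. Percent change is mostly negative in the active arms, so a log needs a shift or a ratio to baseline. A contrast back-transformed from that scale is no longer a difference in arithmetic mean percent change, the quantity on which section 11.2 bases the power and section 11.10 the dose selection. The same sentence also governs the continuous secondary endpoints.

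**Working it through.** **The plan's own figure.** Inputs from section 11.2: 8 patients per active dose, 12 pooled placebo, difference 70, SD 35, "using a one-sided 2.5% level of significance with Hochberg's step-up adjustment for multiplicity of testing".

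- Standard error of one comparison: 35 × √(1/12 + 1/8) = 35 × 0.4564 = 15.97.
- Standardised difference: 70 / 15.97 = 4.38.
- Power of one comparison (normal approximation): Φ(4.38 − 1.96) = 0.992.
- Hochberg over three doses, 200,000 simulated trials, t-tests with variance pooled over four groups: 99.8% for at least one dose and 97.0% for all three. Separate two-group t-tests give 99.7% and 96.1%.

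The protocol states 99% and 97%, so its figures reproduce.

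**How much of the pooled spread is treatment effect.** If a fraction p = 24/36 = 2/3 of patients is shifted by d, the pooled variance is SD² + p(1 − p)d².

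- d = 70, SD 35: 1225 + (2/9) × 4900 = 1225 + 1089 = 2314, of which treatment is 1089/2314 = 47%.
- d = 70, SD 15: 225 + 1089 = 1314, of which treatment is 83%.

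At the planning values the separation is 70/35 = 2 SD. A mixture of two equal-variance normals at that separation still has one peak, which is why the distortion is mild there.

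**How often the check misfires.** Assumptions, since the protocol specifies none: Shapiro-Wilk at 5%, all arms in one test, Week 16 only, exactly normal errors, residuals taken from group means. There were 5,000 trials per row. A rejection is false in every row, because the model holds by construction.

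| Shift in the three active arms | SD | Raw endpoint rejected | Residuals rejected |
|---|---|---|---|
| 0 / 0 / 0 | 35 | 4.6% | 4.5% |
| 70 / 70 / 70 | 35 | 7.6% | 5.0% |
| 60 / 75 / 90 | 35 | 6.7% | 4.9% |
| 90 / 90 / 90 | 35 | 18.3% | 4.6% |
| 70 / 70 / 70 | 25 | 25.4% | 4.8% |
| 70 / 70 / 70 | 20 | 57.5% | 4.9% |
| 70 / 70 / 70 | 15 | 96.8% | 4.8% |
| 90 / 90 / 90 | 20 | 95.0% | 4.3% |

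The simulation error (two standard errors) on the 7.6% is 2 × √(0.076 × 0.924 / 5000) = 0.7 points. Separate runs gave 7 to 8% at the planning values and 25 to 27% at SD 25.

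**Which rows are plausible.** SDs of 25, 20 and 15 do not stand in the documents. Section 4.9 does report about 90% mean serum AAT reduction at 100 and 200 mg after multiple doses in healthy volunteers, with less variability between subjects at the higher dose. Percent change cannot fall below −100. If no active patient rises above baseline, an arm with mean −90 has SD at most √(10 × 90) = 30. An SD below 35 in such arms is therefore plausible, but its size is unknown.

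**Does a switch alter significance?** In 1,500 trials per SD at 70 points, a Yeo-Johnson transformation was applied whenever the pooled test rejected. Among those trials, all three doses had two-sided p < 0.05 in 94% on the raw scale and 94% on the transformed scale at SD 35. At SD 25, 20 and 15 it was 100% on both.

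**The case against.** The case on the other side is substantial.

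- **Small at the plan's own figures.** The excess is 2 to 3 points over the nominal 5%. The large rates need assumed SDs or a 90-point effect in every arm. This stands and limits the size of the point.
- **The text is permissive.** It speaks of evaluating and allows a transformation; it does not require a formal pooled test with an automatic switch. A check within each arm would largely remove the problem. This stands too, but the text does not describe such a check.
- **Normal errors cannot hold exactly.** With an active mean of −70 and SD 35, normal errors would put Φ(−30/35) = 20% of active values below −100%, which is impossible. A reader might infer that any transformation would be unneeded; that is not established. Real skewness or unequal variances are better seen in residuals, because the raw pooled values mix them with the treatment effect.
- **No harm to inference is shown.** A reader might infer that the stated power or the choice of 200 mg is undermined. The documents do not support that: the power reproduces, significance was unchanged in the check above, and the dose was selected on cumulative data from three studies.
- **SAPv3.0 is not available.** The protocol defers detail to the SAP, and the addendum says SAPv3.0 was signed before unblinding. It may already specify residuals or a fixed scale. This stands as a condition on the finding.
- **The Week 16 analysis is done.** For that analysis only reporting can change.

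Back-transformation does not answer the point: it restores the units, not the difference in arithmetic means.

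**Conclusion.** The point holds in a limited form. As written, section 11.10 assesses normality on a quantity that contains the treatment effect, and it leaves the primary scale open to a choice made after seeing the data. Under the assumptions above, false rejection is about 7 to 8% against 5% at the planning values, about 18% at 90 points with SD 35, and about 25 to 97% at 70 points with assumed SDs of 25 to 15. A residual check stays near 5% throughout.

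Two stronger readings are not supported. One is that the better the drug works, the more surely the analysis leaves its scale: the wording allows a transformation but does not mandate one. The other is that every continuous endpoint is affected alike: only the primary endpoint was simulated, and with no treatment effect the raw check rejects at about 5%. No effect on stated power or on the dose choice is shown. The finding rests on the protocol text and falls if SAPv3.0 already specifies a residual check and a fixed scale.

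**What to change.** 1. Confirm first whether SAPv3.0 already covers this. If it does, align section 11.10 with it.
2. Otherwise state that distribution and variance are assessed on residuals of the pre-specified model, viewed by arm as well as overall.
3. Keep percent change from baseline as the primary scale whatever the check shows.
4. Report any transformed analysis only as a sensitivity analysis, named in advance. One candidate is the log ratio to baseline, back-transformed to percent change. It needs a stated rule for values below the limit of quantitation, since section 4.7 describes suppression to that level in healthy volunteers.
5. Apply this to the Extended Efficacy and Final Analyses. For the completed Week 16 analysis, report which scale was used and why.

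The cost is wording and at most one extra table. Sample size, visits and data collection do not change.
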